#### Table GPIA.6.2. Baseline and Postbaseline Definitions for Safety Groups

Abbreviations: ECGs = electrocardiogram; SS = Safety Analysis Set.

a Immunogenicity related analysis is specified in Section 6.13.3.6.

There will be 2 estimands of interest in evaluating primary and key secondary efficacy objectives.

- For objectives controlled for Type 1 error at 52 weeks:
  - the "efficacy" estimand, defined as the average treatment effect of tirzepatide relative to placebo at 52 weeks, in the randomized participants had they remained on their randomized treatment for the entire planned 52 weeks treatment duration.
  - the "treatment regimen" estimand, is the average treatment effect of tirzepatide relative to placebo at 52 weeks, for the randomized participants regardless of the adherence to treatment.

End of study participation for a participant will be the earliest of date of death, date of withdrawal from further participation in the study, or date of safety follow-up visit (Visit 801). For participants considered to be lost-to-follow-up, end of study participation will be the date of lost-to-follow-up reported by the investigator. Participant data included in the database after the last date of study participation (including safety follow-up period) will be excluded from statistical analysis.

Statistical treatment comparisons will only be performed between tirzepatide and placebo. Since the trial is not adequately powered to detect difference among tirzepatide doses, comparisons among tirzepatide doses will not be performed unless otherwise specified.

Statistical summaries and results of statistical analyses will be displayed in the following order: Placebo, tirzepatide 10 mg, tirzepatide 15 mg, and pooled tirzepatide (all doses combined, if necessary).

Not all analyses described in this SAP will necessarily be included in the Clinical Study Reports (CSRs). Any analysis described in this SAP and not provided in the CSR would be available upon request. Not all displays will necessarily be created as a "static" display. Some may be incorporated into interactive display tools instead of or in addition to a static display.

# 6.3. Adjustments for Covariates

The study is stratified by sex (female, male) and presence of comorbidities (Y/N).

Unless otherwise specified, for efficacy related analyses at 52 weeks, sex, presence of comorbidities and corresponding baseline value will be used as a covariate.

# 6.4. Handling of Dropouts or Missing Data

For the primary and key secondary efficacy endpoint analyses subject to type 1 error rate control, data for participants with missing values at the 52-week visit will be imputed based on the method described in Section 6.12.1.1 and 6.12.1.3. However, for the parameters with only 1 postbaseline measure during the analysis period per schedule of activity, the last observation carried forward (LOCF) approach will be applied to impute the endpoint when ED measure is available.

## 6.5. Multiple Comparisons/Multiplicity

The type 1 error rate control strategy for primary and key secondary efficacy objectives is illustrated in Section 6.12.3, which is performed in "efficacy" estimand as efficacy analysis is for China registration purpose. In addition, no multiplicity adjustments will be made for evaluating other secondary and exploratory objectives, and safety assessments.

## 6.6. Patient Disposition

A listing of study disposition for all randomized participants will be provided at the final database lock, respectively. Summaries of study disposition and study drug disposition for all randomized participants will be provided by planned study treatment at the primary database lock (after 52-week treatment).

The study completion status is defined as follows: participants who have completed 52-week treatment period and with non-missing safety follow-up visit (Visit 801) will be considered as completers. Otherwise, they will be considered as non-completers.

# 6.7. Historical Illnesses and Preexisting Conditions

The count and percentages of participants with historical illnesses and preexisting conditions will be summarized by treatment group using the Medical Dictionary for Regulatory Activities (MedDRA) Preferred Term (PTs) nested within System Organ Class (SOC). The SOC will be in alphabetical order. Conditions (that is, PTs) will be ordered by decreasing frequency within SOC. This will be summarized for all randomized participants.

# 6.8. Patient Characteristics

A listing of participant demographics for all randomized participants will be provided. All demographic and baseline clinical characteristics will be summarized by study treatment for all randomized participants. Baseline demographic and clinical characteristics of special interest include but are not limited to: age (years), sex (female, male), height (cm), weight (kg), BMI (kg/m^2), waist circumference (cm), age group (<65 years,  $\geq$ 65 years), BMI group (<28,  $\geq$ 28 kg/m^2); BMI group2 (<30,  $\geq$ 30 and <35,  $\geq$ 35 and <40,  $\geq$ 40 kg/m^2), weight-related comorbidities.

# 6.9. Concomitant Therapy

Concomitant medication will be summarized by PTs by treatment group by decreasing frequency for SS group.

Additionally, medications of interest (as defined below) will be summarized by treatment for SS.

Concomitant medications of interest include the following:

- baseline antihypertensive therapy
- baseline lipid lowering therapy
- changes to baseline medication in post-randomization (in term of type/class and dose):
  - o antihypertensive therapy, and
  - lipid lowering therapy.
- utilization after randomization of:
  - o antidiarrheal medication. and
  - o antiemetic medication.

# 6.10. Treatment Exposure and Compliance

# 6.10.1. Study and Study Treatment Exposure

Summary of duration of follow-up (defined as time in days from date of randomization to the date of the last study visit) and/or duration on study treatment (defined as time in days from date of first dose of study treatment to date of last dose of study treatment plus 7 days) will be provided by treatment group using data from SS in the period of the 52 weeks plus safety follow-up (Visit 801) for all the randomized participants.

For the summary of duration on study treatment, the frequency and percentage of participants falling into the following range will be summarized by planned treatment group as well:

- >0
- $\geq 4$  weeks
- $\geq 8$  weeks
- $\geq 12$  weeks
- $\geq 16$  weeks
- $\geq 20$  weeks
- $\geq 24$  weeks
- $\geq$  36 weeks
- $\geq$ 44 weeks
- $\geq 52$  weeks

In addition, the frequency and percentages of participants falling into the following study treatment exposure ranges may be summarized by planned treatment group:

- 0 weeks
- >0 to <4 weeks
- $\geq 4$  to <8 weeks
- $\geq 8$  to <12weeks
- $\geq 12$  to < 16 weeks
- $\geq 16$  to  $\leq 20$  weeks
- $\geq 20$  to  $\leq 24$  weeks
- $\geq 24$  to <36 weeks
- $\geq$  36 to <44 weeks
- $\geq$ 44 to <52 weeks
- $\geq$  52 weeks

No p-values will be reported in these summaries as they are intended to describe the study populations rather than test hypotheses about them.

# 6.10.2. Compliance to Study Treatment

Summary of prematurely discontinuing study treatment (including discontinuation reason) will be provided by study treatment. A time-to-event analysis of premature study treatment discontinuation will also be conducted.

The analyses related to compliance will be conducted for the period during 52-week treatment period for all randomized participants.

If data warrants, the counts and percentages of participants who follow the planned escalation scheme, have dose interruption, or have dose de-escalation may be summarized for tirzepatide treatment group. In addition, the proportion of participants receiving 2.5 mg, 5 mg, 7.5 mg, 10 mg, 12.5 mg, or 15 mg may be presented by randomized tirzepatide treatment and visit during the dose escalation period.

Treatment compliance will be defined as taking at least 75% of the scheduled tirzepatide doses. Compliance over the study period will be calculated using the number of doses administered (regardless of the actual dose in mg administered) divided by the total number of doses expected to be administered  $\times 100$  over the study period. Treatment compliance will be summarized descriptively in the study period by treatment using the mITT population.

## 6.11. Important Protocol Deviations

Important protocol deviations are identified in the Trial Issues Management Plan (TIMP). A listing and a summary of important protocol deviations by treatment will be provided at the end of 52 weeks treatment (for all randomized participants).

# 6.12. Efficacy Analyses

The assessment of efficacy objectives will be guided by the "efficacy" estimand using the EAS. All primary and key secondary efficacy assessments will be guided by the "treatment regimen" estimand conducted using the FAS for sensitivity analysis. Assessment of the primary and key secondary objectives will be conducted with multiple imputation of missing data (see Section 6.12.1.3).

# 6.12.1. Primary Efficacy Analysis

The primary efficacy measure will be percent change in body weight from randomization **and** percentage of participants who achieve  $\geq 5\%$  body weight reduction at 52 weeks. The percent change in body weight at each nominal visit is defined as:

(postbaseline body weight [kg] – baseline body weight [kg]) / baseline body weight [kg] \* 100%.

Percent change in body weight will be summarized by treatment and nominal visit (week) from randomization to 52 weeks; Percentage of participants who achieve  $\geq$ 5% body weight reduction will be summarized by treatment at 52-week.

## 6.12.1.1. Analysis Related to the Efficacy Estimand

The analysis related to efficacy estimand will be conducted utilizing data in the EAS.

For the mean percent body weight change from randomization, a MMRM will be conducted. Restricted maximum likelihood (REML) will be used to obtain model parameter estimates and the Kenward-Roger option will be used to estimate the denominator degrees of freedom. The response variable of MMRM will be the percent change in body weight from baseline values obtained at each scheduled post baseline visit.

For the percentage of participants achieving at least 5% body weight reduction from randomization over time, a logistic regression model will be used with the response variable of the percentage of participants achieving at least 5% body weight reduction from randomization at 52-week.

For MMRM the independent variables of analysis model are treatment group, visit, treatment-byvisit interaction, stratification factors (presence of comorbidities at randomization, sex) as fixed effects, and baseline body weight as a covariate. An unstructured covariance structure will model relationship of within-patient errors. If this model fails to converge, the following variance covariance structures will be tested in order until convergence is achieved:

- heterogeneous Toeplitz
- heterogeneous first order autoregressive
- heterogeneous compound symmetry
- Toeplitz
- first order autoregressive, and
- compound symmetry.

The first covariance structure that converges will be used.

With the aid of the MMRM analysis, 2-sided 95% CIs for mean percent change in body weight from randomization to the 52-week visit for tirzepatide 10 mg and 15 mg compared to placebo will be derived and summarized. The resulting least squares mean (LSM) estimates of mean percent change in body weight from baseline will be plotted by visit and by study treatment.

A logistic regression model with terms of treatment group, sex, and presence of comorbidities at randomization as fixed effects, and baseline body weight as a covariate, will be conducted for percentage of participants achieving at least 5% body weight reduction from randomization at the 52-week visit. Missing body weight measurement at 52-week will be imputed by the predicted value from MMRM model aforementioned, then the continuous measurements will be dichotomized into status of achieving at least 5% body weight reduction (Yes or No). A logistic regression will be utilized to analyze proportion of participants with at least 5% body weight reduction by treatment at 52-week.

#### 6.12.1.2. Analysis Related to the Treatment regimen Estimand

The analysis related to "treatment regimen" estimand will be conducted using data in the FAS.

The analysis for the mean percent change in body weight will be conducted utilizing ANCOVA. The response variable for the ANCOVA model will be percent change in body weight from randomization at 52 weeks. A logistic regression model will be used for the analysis of the percentage of participants achieving at least 5% body weight reduction obtained at the 52-week visit. Both models will include terms of treatment group, sex, and presence of comorbidities at randomization as fixed effects and baseline body weight as a covariate. The ANCOVA analysis will be conducted with multiple imputation of missing body weight at 52 weeks (see Section 6.12.1.3 for details) and statistical inference over multiple imputation of missing data guided by Rubin (1987). As for the logistic regression, missing body weight data at 52 weeks will be imputed first based on Section 6.12.1.3, then the continuous measurements will be categorized into status of achieving at least 5% body weight reduction (Yes or No).

With the aid of the ANCOVA model, 2-sided 95% CI for mean change in percent body weight from baseline to the 52-week visit between tirzepatide 10 mg and placebo, as well as tirzepatide 15 mg and placebo will be derived.

With the aid of the logistic regression model, 2-sided 95% CI and odds ratio for percentage of participants achieving at least 5% body weight reduction from baseline to the 52-week visit between tirzepatide 10 mg and placebo, as well as tirzepatide 15 mg and placebo will be derived.

## 6.12.1.3. Methods for Multiple Imputations

For efficacy analyses relative to "treatment regimen" estimand, the intercurrent events (ICEs) and the resulting missing values will be handled as follows:

- Category 1: for missing data solely due to exceptional circumstances, such as pandemic or natural disasters (after other reasons for missing data are ruled out), the analysis will consider the missing data as missing at random. The missing data will be imputed using all non-missing data of the primary outcome measurement from the same treatment arm.
- Category 2: for missing data due to all other ICEs: missing data will be imputed based on retrieved dropouts in the same treatment arm, defined as observed primary outcome measurements, from participants in the same treatment group, who had their efficacy assessed after early discontinuation of the study drug. In case where there are not enough retrieved dropouts to provide a reliable imputation model (for example, the model implemented by the SAS program does not converge), an alternative multiple imputation method with reference to the placebo group (that is, placebo multiple imputation) will be used.

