- e For participants who discontinue or complete the study within 52 weeks, Visit 801 (safety follow-up visit) should be performed 4 weeks after the last visit during the 52-week treatment period.
- f The visit date is determined in relation to the date of the randomization visit (\pm the allowed visit window).
- g Medical history includes assessment of preexisting conditions (including history of gall bladder disease, cardiovascular disease, and medullary thyroid carcinoma) and substance usage (such as alcohol and tobacco).
- h Weight measurements should be obtained per the instructions in Appendix 8. Body weight must be measured in fasting state. If the participant is not fasting, the participant should be called in for a new visit within the visit window to have the fasting body weight measured.
- i ECG should be collected at least 30 minutes prior to collection of blood samples for laboratory testing, including PK samples.
- J Vital sign measurements should be taken before obtaining an ECG tracing and before collection of blood samples for laboratory testing, per the instructions in Appendix 8.
- k All training should be repeated as needed to ensure participant compliance.
- Counselling on diet and exercise, to be performed by a dietician or equivalent qualified delegate, to include calculation of individualized energy requirement and methods to change dietary composition and amount of physical activity. The Lifestyle Program Instruction may be delivered on a separate day from the rest of that visit's study procedures but must occur within the visit window. Beginning at Week 8, the Lifestyle Program Instruction may be delivered by phone.
- m Study personnel to provide reinforcement and encouragement for lifestyle modifications.
- n Participants should administer their first dose of study drug on site at the end of the Visit 2, after other study procedures are completed.
- O A serum pregnancy test will be performed at Visit 1 for women of childbearing potential only.

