#### Sample size determination

Approximately 210 participants will be randomly assigned to study intervention (70 participants per intervention group). The sample size determination assumes that evaluation of superiority of tirzepatide 10 mg and tirzepatide 15 mg to placebo will be conducted in parallel, each at a 2-sided significance level of 0.025 using a 2-sample t-test. Additionally, a difference of at least 11% mean body weight percentage reduction from randomization at 52 weeks for tirzepatide 10 mg and/or tirzepatide 15 mg compared with placebo, a common standard deviation (SD) of 11%, and a dropout rate of 25% are assumed for statistical power calculations. Under the assumptions above, randomizing 210 participants in a 1:1:1 ratio to tirzepatide 10 mg (70), tirzepatide 15 mg (70), and placebo (70) provides more than 90% power to demonstrate superiority of each tirzepatide dose to placebo.

The chosen sample size and randomization ratio also provides >90% power to establish superiority of tirzepatide 10 mg and tirzepatide 15 mg doses to placebo in term of proportion of participants achieving at least 5% body weight reduction at 52 weeks, conducted in parallel using a Chi-square test, each at a 2-sided significance level of 0.025, assuming 25% placebo-treated participants and 90% tirzepatide-treated participants achieving the goal and a dropout rate of 25%.

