## 6.12.1.4. Sensitivity Analysis Related to the Treatment regimen Estimand

Sensitivity analyses of the primary efficacy outcomes will be conducted using the FAS and guided by the "treatment-regimen" estimand, which represents the efficacy irrespective of adherence to study drug. This assessment will analyze percent change in body weight obtained at the 52-week visit using an ANCOVA and the percentage of participants achieving at least 5% body weight reduction obtained at the 52-week visit using a logistic regression model. The terms for both models will be the same as specified in Section 6.12.1.2 for "treatment regimen" estimand.

Missing values of change in body weight at the 52-week visit will be imputed based on observed body weight change from baseline values at the visit from participants in the same treatment group who had their efficacy assessed after early discontinuation of study drug. In cases where there are not enough retrieved dropouts to provide a reliable imputation model (for example, the model implemented by the SAS program does not converge), an alternative multiple imputation method with reference to the placebo group (placebo multiple imputation) will be used. Analysis will be conducted with multiple imputations.

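### For the treatment-regimen sensitivity estimand, SAP 6.12.1.3 picks imputation donors by why week-52 weight is missing, not by whether the participant was still on drug

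*SAP*

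**What the plan says.** SAP 6.2 defines the treatment-regimen estimand as the week-52 effect "for the randomized participants regardless of the adherence to treatment". SAP 6.12 analyses it on the FAS as a sensitivity analysis for the primary and key secondary endpoints. SAP 6.12.3 places type 1 error control on the efficacy estimand alone.

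SAP 6.4 states that "data for participants with missing values at the 52-week visit will be imputed based on the method described in Section 6.12.1.1 and 6.12.1.3". Section 6.12.1.1 serves the efficacy estimand, so a missing value under the treatment-regimen estimand goes to 6.12.1.3. SAP 6.12.1.2 sends it there too. That section has two categories:

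- **Category 1**, where exceptional circumstances are the only cause of missingness and other causes have been excluded: "The missing data will be imputed using all non-missing data of the primary outcome measurement from the same treatment arm".
- **Category 2**: "missing data due to all other ICEs: missing data will be imputed based on retrieved dropouts in the same treatment arm". Retrieved dropouts are participants measured after stopping study drug. If there are too few to fit a model, the fallback is multiple imputation with reference to placebo.

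SAP 6.12.1.4 drops the two categories: "Missing values of change in body weight at the 52-week visit will be imputed based on observed body weight change from baseline values", again taken from same-arm participants measured after stopping drug, with the same fallback. None of these rules mentions the drug status of the participant whose value is being filled in.

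**The concern.** An estimand that takes adherence as it falls needs each missing weight drawn from people in the same adherence state. Reason for missingness is a poor proxy for that state.

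A participant can still be injecting at week 52 and have no usable weight. Visit 15 may be missed, or the participant may arrive unfasted. Protocol Section 2, footnote h, says "If the participant is not fasting, the participant should be called in for a new visit within the visit window", but that recall can fail. If the cause is not exceptional circumstances, only Category 2 remains, and its donors are off drug. If a missed visit is not counted as an intercurrent event, 6.12.1.3 has no rule at all, and the programmer must invent one. Section 6.12.1.4 leaves no such doubt: this participant gets off-drug donors, and so does an adherent participant whose weight was lost to a lockdown.

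At stake is how well the sensitivity analysis represents its own estimand. It is meant to show how the primary result holds up when actual adherence is respected. Treating adherent participants as off drug understates that effect.

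**Working it through.** **1. The plan's own power figure.** Inputs from the SAP sample size section: "each at a 2-sided significance level of 0.025 using a 2-sample t-test"; "a difference of at least 11% mean body weight percentage reduction from randomization at 52 weeks"; SD 11%; 70 per arm; 25% dropout.

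- Evaluable per arm: 70 × 0.75 = 52.5.
- Noncentrality: 11 / (11 × √(2/52.5)) = 5.12, with 103 degrees of freedom.
- Power: 99.8%. The stated figure of more than 90% reproduces.

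**2. Where each kind of missing value goes.**

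| Drug status at week 52 | Reason missing | Donors in 6.12.1.3 | Donors in 6.12.1.4 |
|---|---|---|---|
| On | Exceptional circumstances | Whole arm | Off drug |
| On | Other | Off drug, or no rule | Off drug |
| Off | Exceptional circumstances | Whole arm, or off drug, depending on the reading | Off drug |
| Off | Other | Off drug | Off drug |

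In 6.12.1.3 the second row is mismatched or undefined and the third is ambiguous. In 6.12.1.4 both on-drug rows are mismatched.

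**3. Shift per adherent participant given off-drug donors.** The shift in an arm mean is gap / 70, where the gap is the difference in mean percent weight change between on-drug and off-drug participants. The documents do not give the gap, so I assume 5 to 11 points. The upper end equals the SAP's assumed difference from placebo. It would apply if off-drug donors look like placebo or the placebo-referenced fallback is used.

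- 5 / 70 = 0.07 points; 11 / 70 = 0.16 points.
- For four such participants (an illustrative count): 4 × 5 / 70 = 0.29 and 4 × 11 / 70 = 0.63 points.
- For the ≥5% responder rate, using the SAP's planning rates of 90% and 25% as the extreme case: (90 − 25) / 70 = 0.93 percentage points per participant.

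The shift carries over to the treatment difference if the on/off-drug gap in the placebo arm is near zero, which is also an assumption.

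**4. Category 1, if it is read to include participants who had already stopped drug.** Read the 25% dropout as drug discontinuation; the SAP does not say which kind it is. Let r be the share of off-drug participants with a week-52 weight. The on-drug share of donors is 52.5 / (52.5 + 17.5r).

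- r = 1: 75%. r = 0.5: 86%. r = 0.2: 94%.
- The shift per participant is gap × on-drug share / 70, from 5 × 0.75 / 70 = 0.05 to 11 × 0.94 / 70 = 0.15 points. It overstates weight loss.

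**5. Does superiority depend on this?** Take 10% of an arm (7 of 70) misrouted with an 11-point gap. The shift is 0.10 × 11 = 1.1 points, so the assumed effect falls from 11 to 9.9. With 52.5 per arm at two-sided 0.025, power is 99.1% (normal approximation).

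**The case against.** The strongest reply concerns role and scale. This is a sensitivity estimand, and the group concerned is narrow. Study drug comes only through the trial (Protocol Table GPIA.3), so anyone who leaves the study is off drug and Category 2 suits them. What remains is people still dosing with no fasting weight within ±7 days despite the recall rule, and Protocol Appendix 10 can widen the window to 14 days before and 28 days after in exceptional circumstances. The numbers of misrouted participants and the gap are assumed. The SAP also does not rule out conditioning on prior weights, which could shrink the error. All of this stands and limits the size of the point. It does not supply a correct rule for the adherent participant.

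A second reply concerns Category 1. It is limited to data missing for exceptional circumstances alone, once other causes are excluded. Stopping drug is itself an intercurrent event, so an off-drug participant whose Visit 99 was lost to a lockdown may belong in Category 2. A reader might infer a definite opposite bias; the text does not support that. It supports only an ambiguity. The limiting words concern causes of missingness, and having stopped drug need not be why a visit was missed. SAP 8.7 sends COVID-19 missing data to this section without resolving the matter.

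A third reply concerns the remedy. A flag for not having permanently discontinued could sweep in people lost to follow-up with no recorded stop date and give them on-drug values. That would inflate the effect. This is right, and the fix below allows for it.

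A reader might also infer from the general sentences in SAP 6.4 and 6.12 that the primary analysis uses this rule. It does not: 6.12.1.3 opens by limiting itself to the treatment-regimen estimand, and 6.12.1.1 relies on the MMRM and its predicted values.

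**Conclusion.** The point holds as a defect in a sensitivity analysis. SAP 6.12.1.3 gives an adherent participant with an ordinary missing week-52 weight either the wrong donors or no rule, and 6.12.1.4 gives off-drug donors to every missing value. The direction is towards a smaller regardless-of-adherence effect. The size is about 0.07 to 0.16 points per misrouted participant in an arm of 70, resting on the assumed 5 to 11 point gap and on draws that do not use the participant's prior weights. The Category 1 error is possible, of similar size and opposite sign, and depends on how its limiting words are read.

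It would go too far to say that the trial cannot state its effect regardless of adherence. The plausible shifts are small against an assumed 11-point difference. The efficacy-estimand analysis, its error control and the superiority conclusion are untouched. The change is still worth making before database lock, because SAP 6.2 names this as one of two estimands for the primary and key secondary objectives and the correction is cheap.

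**What to change.** Rewrite the two categories in SAP 6.12.1.3 by drug status, and apply them to the key secondary endpoints as well:

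1. **Documented as still on study drug at week 52** (last dose date plus 7 days covers the visit, or the last contact shows continued dosing). Impute under missing at random from on-drug participants of the same arm, using the participant's own prior weights, whatever the reason for missingness.
2. **Permanently discontinued, left the study, lost to follow-up, or drug status unknown.** Impute from same-arm retrieved dropouts, with the existing placebo-referenced fallback, whatever the reason, pandemic included. This class takes precedence where both descriptions could fit.

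For the week-20 weight endpoint, take status at week 20. This wording removes the uncertainty over whether a missed visit is an intercurrent event and the ambiguity in Category 1.

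Leave the method in 6.12.1.4 unchanged, but label it a conservative analysis that treats all missing values as off drug. It then keeps a purpose distinct from 6.12.1.2.

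The cost is SAP wording, two imputation models, and one flag derived from dosing dates already collected. The EAS already uses the 7-day cut-off, and weights are scheduled up to week 44 to support the on-drug model. No new data are needed.
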